2.2. Objectives

The primary objective of the trial is to evaluate the effectiveness of gabapentin to decrease pain and irritability in children with SNI, when the source of pain and irritability is attributed to neurological dysregulation (nociplastic pain), as measured by parent reported pain scores. This objective corresponds to the primary outcome listed in section 3.4.1.

We will compare the gabapentin versus placebo along an escalating dose range for both individual subjects and for the group. We will aggregate the results of the completed N-of-1 trials across all subjects to estimate the group level comparative effectiveness of gabapentin in reducing pain and irritability.

The secondary objectives are to:

- 1. Identify the optimal dosing of gabapentin in reducing pain and irritability (Corresponds to secondary outcomes 3.4.2 and 3.4.3).
- 2. Identify the latency time for gabapentin to show effectiveness (Corresponds to secondary outcome 3.4.4).
- 3. Evaluate the safety and tolerability of gabapentin (Corresponds to secondary outcome 3.4.5).
- 4. An Exploratory objective will be to evaluate whether parent/caregiver stress and function improve if gabapentin reduces children's pain and irritability. This objective corresponds to the Exploratory outcome listed in section 3.4.6.

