Gabapentin is clinically started at a low dose and increased until either effectiveness is demonstrated or an upper limit dose, derived empirically, is reached. Based on work by [name] and Solodiuk we have established a dose titration schedule that will reach a typically effective dose over 15 days ([name], personal communication).⁴⁴ Extensive expert opinion shows that in the setting of children with neurological irritability and pain, as opposed to functional chronic pain in other children/youth, the onset of pain relief is much more rapid than several weeks. Ref. 49 describes improvement in pain scores (NPASS) in a neonatal cohort at 14 days. In another study, an RCT of gabapentin in children, a stable dose was reached at 22 days, and clinical effect was seen within that time frame, even though the protocol continued to 30 days. [Effectiveness of Gabapentin on Chronic Irritability in Neurologically Impaired Children. ClinicalTrials.gov Identifier: NCT01675960. The trial was terminated due to slow recruitment (2 enrolled)]. In personal communication with the study PI, ([name]), most of the effect was actually within 2 weeks and this is confirmed in his clinical practice. [name], author of Ref 41, 43 and 44 concurs with this time frame, in personal communication. Parent-caregivers will administer either active gabapentin or placebo on the same schedule. When transitioning between gabapentin and placebo, in either direction, there will be a 3-day washout period. A study dosing table is shown in Section 3 3

The primary variable assessed is the child's pain score. Pain and irritability will be measured using the Non-Communicating Children's Pain Checklist – Revised (NCCPC-R) at specified intervals throughout the randomized sequence of G: P. Additional measures of parent/caregiver burden and impact on their daily function will be undertaken weekly with the PROMIS-57, a tool adapted to measure the impact of the child's pain and irritability on parental functioning. This multi-dimensional tool assesses the parent/caregiver's stress, activity, function and sleep and is a proxy for the distress caused by the child's condition.

Other measures will be of usual, known side effects (e.g., sedation) and of any unexpected adverse events. Known side effects will be assessed regularly at the start, mid-point and end of each sequence via the Health Update. Unexpected adverse events will be tracked continuously.

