Summary: This study uses a rapid and safe dose escalation to the widely accepted therapeutic range where evaluation of response will be undertaken with frequent scoring. Different maximal doses are used for children < or ≥ 15 kg, based on pharmacokinetic data. Doses are titrated to clinical effect or maximum target dose, whichever is lower. Once in the therapeutic range, doses change after 3 days if there is not an adequate reduction in symptoms. For any subject that obtains clinical benefit below maximal dose, then they will be held at that dose for the remainder of that period until such time as the scheduled wean begins. At the end of each treatment period there is a wash-out.

Starting Dose: The starting dose of gabapentin will be 5 mg/kg administered as oral liquid or via gastric or jejunal routes. On Day 1 of the study, the gabapentin will be administered once at bed-time and then increased according to the schedule shown in Table 1.

Dose Escalation: The dose will be increased every 3^{rd} - 4^{th} day in a step wise fashion of 13% - 50%, starting with the evening dose in order to accommodate sedation. The maximum dose for subjects will be as follows: < 15 kg to 60 mg/kg day and \geq 15 kg to 45 mg/kg/day. Dose titration will be to a maximum target dose (based on weight as described, < 15 kg, > 15kg) or to clinical effect, whichever is lower. The dose escalation scheme is based upon expert consensus and personal communication with [name], [name], and upon review with the BC Children's Hospital research pharmacist. \cdot , 56.

Some children with PIUO and SNI have been given gabapentin empirically by their health care provider, often without any subsequent, detailed assessment of benefit. Many times, the medication is continued because of its low side-effect profile and overall safety compared with other analgesics. If a subject is currently on gabapentin at the time of enrolment, and the parent/caregiver wants an evaluation of its effectiveness, then the subject can be enrolled in this study with the following approach:

After appropriate enrolment and consent, the subject will be weaned off of gabapentin, in a stepwise manner with 25% reductions in dose every 3rd day. Once they are no longer on the active drug, they will be randomized to active drug or placebo like all other study participants.

Gabapentin Risks and Precautions

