3.4. Outcomes

1. Primary Outcome: The mean pain and irritability score on the NCCPC-R through days 11-19 on active drug compared to placebo.

[figure not shown]
An 11-point decrement in the NCCPC-R score with no rebound x 3 days is considered clinically meaningful minimum change (improvement).

Secondary Outcomes:

- 2. For patients who benefited from gabapentin, identification of the lowest dose that was effective in reducing pain scores, as shown by a improvement the NCCPC-R score compared to baseline during day 11-19 on active drug.
- 3. For patients who benefited from gabapentin, identification of the maximal effect dosage as measured by the largest improvement in the NCPCC-R score compared to baseline during days 11-19 on active drug.
- 4. Identification of the latency time in days to the onset of maximum relief of pain and irritability as measured by the NCCPC-R score over days 0-19.
- 5. Adverse Events Collection demonstrates the AE on treatment arm do not exceed the frequency found in the Product Monograph for children receiving gabapentin.
- 6. Exploratory Outcome: PROMIS-57 scores reported by parent/caregiver are improved on the treatment arm compared to the placebo arm.

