3.10. Statistical Methods

All data will be entered into a REDCap database, either directly from participants using a web-based entry system, or for those using paper, transferred from data collection sheets by a research assistant. The study cohort will be described in tables with descriptive statistics (mean, median and standard deviation) where appropriate. The primary method of analyzing the data was by systematic visual graphing of the pain scale over the exposure/placebo conditions. This is the method recommended by the CONSORT collaboration, extension for N-of-1 studies (CENT).⁵⁸

Data analysis for the primary outcome will be conducted within each N-of-1 trial and will also be aggregated across trials using measurements taken on days 11-19.

For each individual, the pain and irritability score on the NCCPC-R will be calculated over days 11-19 for both the treatment and control periods. These means will then be compared statistically using a Bayesian model, reporting the posterior mean difference using a non-informative prior for the means and variance. The posterior probability that the mean of the treatment is greater than the mean of the control will also be reported. Because of the use of non-informative priors, this analysis is very similar to a t-test.

We will also aggregate the means across participants using Bayesian linear mixed models in order to compare the average effect of the treatment as well as obtain better estimates of each individual's effect through borrowing of strength from others' data.

Additional analyses

Secondary outcomes will be assessed as follows:

- For each patient who benefits from gabapentin, the lowest dose that was effective in reducing pain scores will be calculated as the lowest dose that gives at least an 11 point reduction with no rebound over 3 days in the NCCPC-R score compared to baseline during day 11-19 on active drug. The set of lowest doses will be summarized descriptively.
- For each patient who benefits from gabapentin, the maximal effect dose will be calculated as the dose that gives the largest improvement in the NCPCC-R score compared to baseline during days 11-19 on active drug. The set of lowest doses will be summarized descriptively.

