- The latency time in days to the onset of maximum relief of pain and irritability as measured by the NCCPC-R score will be the day that gives the largest improvement in the NCPCC-R score compared to baseline during days 0-19 on active drug. The set of latency times will be summarized descriptively.
- Adverse Events will be compared between treatment arms descriptively.
- PROMIS-57 scores reported by parent/caregiver will be computed for each patient on each arm by averaging the scores taken on days 12, 16 and 19 and comparing these mean scores. The differences in mean scores between the treatment and placebo arms will be summarized descriptively.

Analysis population and missing data

For the primary outcome, any missing days will be excluded from calculation of the mean.

For secondary outcomes, missing values will be disregarded in the sense that only observed values will be used to compute the lowest dose, maximal effect dose, latency time and PROMIS-57 mean scores.

Analyses will use the intent-to-treat principle meaning that observations in a period will be ascribed to the treatment to which that period was randomized.

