^{*}If the child participated in the PIUO Study within the last 6 months these items will already be completed and only a Health Update is necessary to complete prior to drug dispensing. If the child did not participate in the PIUO Study all items will be completed and the PIUO Pathway will be implemented prior to drug dispensing. If a treatable cause for the child's PIUO is uncovered, the child will be withdrawn from the gabapentin trial.

Version 3.0 October 4, 2020 Page 39 of 45

 Table 4: Medication and Placebo Assessment Schedule for all subjects

Day	Health Update	Concomitant Medications	NCCPC-R	Pain Survey	PROMIS-57
1	X	X	X	X	X
2					
3					
4					
5			X	X	
6					
7					
8			X		
9					
10					
11	X		X		
12			X	X	X
13			X		
14			X		
15			X		
16			X	X	X
17			X		
18			X		

Version 3.0 October 4, 2020 Page 40 of 45

19			X	X	X
20					
21					
22			X		
23					
24					
25					
Switch Over*	X	X	X	X	X

^{*}Day 1 or 26 if switching over, not both

Version 3.0 October 4, 2020 Page 41 of 45

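### Latency defined as the single best-scoring day, for every child, cannot tell early relief from no effect and so does not answer secondary objective 2

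*Protocol*

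**What the plan says.** Section 2.2 gives the second secondary objective as "Identify the latency time for gabapentin to show effectiveness". Section 3.4 turns this into outcome 4, "Identification of the latency time in days to the onset of maximum relief of pain and irritability", over days 0-19. Section 3.10 fixes the calculation: latency "will be the day that gives the largest improvement in the NCPCC-R score compared to baseline during days 0-19 on active drug", and the set of values is then summarised descriptively.

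Three further statements matter.

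- **Population.** Both dose outcomes in section 3.10 are limited to responders, for example "For each patient who benefits from gabapentin, the maximal effect dose will be calculated as the dose". The latency rule has no such limit, in section 3.10 or in section 3.4.
- **Scoring days.** Table 4 in section 6.2, the "Medication and Placebo Assessment Schedule for all subjects", places the NCCPC-R on day 1, days 5 and 8, every day from 11 to 19, day 22 and the switch-over. Section 3.10 uses observed values only, so an unscored day can never be the latency day.
- **Benefit threshold.** Section 3.4 defines a meaningful change: "An 11-point decrement in the NCCPC-R score with no rebound x 3 days". The latency rule does not use it.

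**The concern.** The objective asks how long the drug takes to show an effect. The rule finds the day of the lowest score. If a child improves early and stays improved, every later day has the same expected score and noise decides which is lowest. That profile is plausible here: under section 3.3, a child who benefits below the maximal dose stays there, "then they will be held at that dose for the remainder of that period".

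A child who never improves also has a lowest score, and so enters the summary with a latency. Nothing in the calculation shows what the same rule would return on placebo.

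The protocol intends its results to help design a larger trial. A latency figure that looks the same under early relief and under no effect is a poor input for that.

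**Working it through.** The protocol states no expected latency, so there is no figure to reproduce. The check asks what the rule returns under known onset times.

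**Inputs.** From Table 4, the post-baseline scored days up to day 19 are 5, 8, 11, 12, 13, 14, 15, 16, 17, 18 and 19: two in days 2-10 and nine in days 11-19. Section 3.6 says that no data on day-to-day variability were available, so standard deviation, correlation and size of relief are assumptions.

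**Exact result for a flat profile.** With independent noise and a constant expected score, each scored day is equally likely to be the best, whatever the standard deviation.

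- Mean = (5 + 8 + 11 + ... + 19)/11 = (13 + 135)/11 = 148/11 = 13.45.
- Median = the 6th of 11 ordered values = day 14.
- Share on day 11 or later = 9/11 = 82%.

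This is the no-effect result. Sustained relief from day 3 gives the same result, because all 11 scored days then lie on the plateau. Simulation agrees: steps of 11 or 20 points with SD 4 or 8 give mean 13.5 and median 14, and a 15-point step with SD 10 gives mean 13.4 and median 14.

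**What the rule contributes and what the schedule contributes.** Apply the same rule to a full daily grid, days 2-19.

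- No effect: (2 + 19)/2 = 10.5.
- Relief from day 3: (3 + 19)/2 = 11.0.

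Even with daily scoring the two cases differ by only half a day. The sparse early schedule adds 13.45 - 11.0 = 2.45 to 13.45 - 10.5 = 2.95 days.

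**Later onset.** When relief is large relative to noise, the best day falls among the scored days after onset.

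| Relief from | Scored days on plateau | Exact mean | Simulated mean |
|---|---|---|---|
| Day 7 or 8 | 8, 11-19 | 143/10 = 14.3 | 14.2 to 14.3 |
| Day 10 or 11 | 11-19 | 135/9 = 15.0 | 14.9 to 15.0 |
| Day 14 | 14-19 | 99/6 = 16.5 | 16 to 16.5 |
| Day 17 | 17-19 | 54/3 = 18.0 | 17 to 18 |

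**Sensitivity.**

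- Lag-1 correlation of 0.3 to 0.8, day 1 excluded: the mean falls from 13.2 to 12.5 and the median from 14 to 13, the same for no effect and for day-3 relief.
- Day 1 allowed as the best day, no effect: mean (148 + 1)/12 = 12.4, median 13.5.
- Day 1 allowed and correlation 0.8, no effect: mean 10.9, median 12. This is the lowest case.

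**Other rules on the existing schedule** (assumed 15-point step, independent noise).

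- Best day, but only in children with three consecutive 11-point reductions in days 11-19: relief from day 3 still gives mean 13.5 to 13.6 and median 14.
- First scored day with an 11-point reduction, in the same children: relief from day 3 gives median 5 (mean 5.6 at SD 4, 6.0 at SD 10). At SD 4, onset on day 7, 10 or 14 gives median 8, 11 or 14.

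**The case against.** The best case for the plan is that outcome 4 speaks of maximum relief, and the best-scoring day matches that wording. Dense scoring on days 11-19 is deliberate, because section 2.3 expects a typically effective dose to be reached over 15 days. Full relief by day 3 would be early in the titration. The outcome is secondary and descriptive in ten children, and section 3.10 makes visual graphing the main method, so each child's actual profile will be seen.

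Most of this stands as a limit on the point. It does not rescue the rule: outcome 4 is mapped to an objective about time to effect, non-responders still contribute values, and the reported number remains misleading even if the graphs are clear.

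A reader might infer more than the protocol supports, in four ways.

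- *The schedule alone produces day 14.* It does not. On a daily grid the rule still gives 10.5 and 11.0, so the best-day definition causes the failure to separate the two cases and the schedule only shifts the value.
- *Any definition of latency would fail on this schedule.* A first-crossing rule on the same days gives a median of day 5 for day-3 onset.
- *The measure is blind to onset altogether.* It moves to 15-18 days as onset moves from day 10 to day 17.
- *A result near 14 would falsely confirm the expectation in section 2.3.* The phrase there, "most of the effect was actually within 2 weeks", is an upper bound on most of the effect and does not predict maximum relief on day 14.

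**Conclusion.** The point holds in a limited form. As defined, latency cannot distinguish early sustained relief from no effect: both give a mean of about 13.5 and a median of 14. It therefore does not answer secondary objective 2. The chief cause is the best-day rule. Including children without benefit and omitting a placebo comparison hide the problem, and sparse early scoring adds about 2.5 to 3 days.

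The figures assume that relief, once present, stays flat, that noise is independent from day to day, and that day 1 serves only as baseline. Relaxing the last two brings the mean to about 11-13. Relief that deepens with dose gives later values, and in that case the measure carries some information. The consequence is confined to a descriptive secondary outcome and its use in planning the larger trial.

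**What to change.** Replace the latency definition in section 3.10, and align outcome 4 in section 3.4 with it.

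1. Compute latency only for children who meet the protocol's own 11-point benefit rule. Report the others as having no latency, and give their number.
2. Define latency as the first scored day with at least an 11-point reduction from baseline that is maintained at the following scored assessments. State in advance how many assessments that means and which score is the baseline in each period.
3. Report it as the interval since the previous scored day: 1-5, 5-8, 8-11, then daily.
4. Show the identical calculation for each child's placebo period beside the active one.

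Limiting the present rule to responders is not enough, since day-3 relief would still be reported at about day 14. Extra NCCPC-R scores in days 2-10 would narrow the early intervals. They are optional and do not cure the best-day rule.

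The cost is wording only, since all the scores are already scheduled. Fewer children will contribute a latency, and onset before day 11 is resolved only to the intervals above. With large day-to-day noise a first-crossing day can fall too early, which is why the maintenance condition and the placebo comparison are both needed.

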3.11. Data Monitoring

Formal Committee

The Gabapentin Trial will be monitored by a Data Safety Monitoring Board (DSMB), nestled under the Research Network CHILD-BRIGHT, sponsoring this trial. The DSMB will review the reports created by the study team on a bi-annual basis. Based on review of the reports, the DSMB may consider making recommendations on the adverse events, protocol deviations and ongoing monitoring of the data as assembled. The duties, activities and referential framework for the DSMP will be laid out in the Data Safety Monitoring Plan.

Monitoring

The study site agrees to allow the Sponsor-Investigator's monitor(s) direct access to the study records and medical records from those patients enrolled in the clinical study as well as drug accountability records. Monitoring for this study will consist of data management review focused on erroneous data, illogical entries, and missing data, and on central monitoring of clinical and operational data reviewed for outliers and trends. On-site monitoring will be targeted based on the results of data management and of central monitoring reviews. A site initiation, with the presence of the site monitor, will ensure that best Good Documentation Practices (GDP) are set up. A site visit when half of the participants have been enrolled and at study close out will follow the site initiation and ensure that GDP is being followed and that reporting on protocol deviations or adverse events during the trial has been done when necessary.

Plans for Site Monitoring are laid out in the Data Safety Monitoring Plan.

Early Termination of the Trial

As part of their duties to ensure that research participants are protected, the institutional REB or other government organizations may discontinue the study at any time. Regulatory authorities and the Sponsor-Investigator retain the authority to suspend additional enrollment for the entire study as applicable.

3.12. Safety/Harms

The safety analyses will include all data with no exclusions allowed because of protocol deviations.

Definition of Adverse Events

An AE is any untoward medical occurrence in a patient or clinical investigation participant, administered a study medication/intervention, which does not necessarily have a causal relationship with this treatment. An AE can therefore be any unfavorable and unintended sign (including an abnormal laboratory finding), symptom, or disease temporally associated with the use of a medicinal (investigational) study medication/intervention, whether or not related to the medicinal (investigational) study medication/intervention.

During each contact with the participant and the participant's caregiver, information on AEs will be gathered and documented accordingly. AEs will be graded as mild, moderate, severe or life threatening and assessed by causality as probably related, possibly related, unlikely to be related or not related to the study drug.

Other clinically significant AEs are those that cause the study participant discomfort or interfere with normal functions such as feeding, sleep, activity, etc. In this study these are likely to be the new onset of known side effects of gabapentin, as listed in the Health Update, or any other events that the parent-caregiver is concerned about.

Definition of Serious Adverse Events

An SAE is defined as an AE meeting one of the following criteria at any dose:

• Results in death during the period of protocol-defined surveillance

- Is a life-threatening event (defined as a participant at immediate risk of death at the time of the event)
- Results in in-patient hospitalization or prolongation of existing hospitalization during the period of protocol-defined surveillance
- Results in persistent or significant disability or incapacity. (Disability is defined as a substantial disruption of a person's ability to conduct normal life functions)

Any other important medical event that may not result in one of the above outcomes, may be considered a SAE when, based upon appropriate medical judgment, the event may jeopardize the participant and may require medical or surgical intervention to prevent one of the outcomes listed above. Examples of such medical events include allergic bronchospasm requiring intensive treatment in an emergency room or at home, blood dyscrasias or convulsions that do not result in inpatient hospitalization, or the development of drug dependency or drug abuse.

Participants will be monitored during the 108-day study period for SAEs. If an SAE is ongoing at the time a participant discontinues/completes the study, the SAE will be followed until the Investigator agrees that the event is satisfactorily resolved, becomes chronic, or that no further follow-up is required.

Stable chronic conditions which are present prior to clinical trial entry and do not worsen are not considered AEs and will be accounted for in the participant's medical history.

Relationship to Treatment

For all collected AEs (including SAEs), the clinician who examines and evaluates the participant will determine the AE's causality based on temporal relationship and his/her clinical judgment.

In some circumstance, an AE will require the unblinding of the trial. The study pharmacist will inform the Study Medical Monitor as to whether the active medication or the placebo was in use. The Medical Monitor can then advise the Investigator as to whether the subject should be withdrawn from the study, a modification made in the drug schedule, or no action needs to be taken.

The degree of certainty about causality will be graded using the categories below:

Definitely Related: There is clear evidence to suggest a causal relationship, and other possible contributing factors can be ruled out. The clinical event, including an abnormal laboratory test result, occurs in a plausible time relationship to drug administration and cannot be explained by concurrent disease or other drugs or chemicals. The response to withdrawal of the drug (de-challenge) should be clinically plausible. The event must be pharmacologically or phenomenologically definitive, with use of a satisfactory re-challenge procedure if necessary.

Probably Related: There is evidence to suggest a causal relationship, and the influence of other factors is unlikely. The clinical event, including an abnormal laboratory test result, occurs within a reasonable time sequence to administration of the drug, is unlikely to be attributed to concurrent disease or other drugs or chemicals, and follows a clinically reasonable response on withdrawal (de-challenge). Re-challenge information is not required to fulfill this definition.

Possibly Related: There is some evidence to suggest a causal relationship (e.g., the event occurred within a reasonable time after administration of the trial medication). However, the influence of other factors may have contributed to the event (e.g., the participant's clinical condition, other concomitant events). Although an adverse drug event may rate only as "possibly related" soon after discovery, it can be flagged as requiring more information and later be upgraded to "probably related" or "definitely related", as appropriate.

Unlikely: A clinical event, including an abnormal laboratory test result, whose temporal relationship to drug administration makes a causal relationship improbable (e.g., the event did not occur within a reasonable time after administration of the trial medication) and in which other drugs or chemicals or underlying disease provides plausible explanations (e.g., the participant's clinical condition, other concomitant treatments).

Not related: The AE is completely independent of study drug administration, and/or evidence exists that the event is definitely related to another etiology. There must be an alternative, definitive etiology documented by the clinician.

Intensity

The Intensity (severity) for each AE (including SAE) will be graded according to the RN or MD who examines and evaluates the participant, given the clinical team's experience with severely disabled children, as mild, moderate or severe and potentially life-threatening.

Reporting

Only SAEs that meet the definition of an unanticipated problem (i.e. unexpected, related and involving greater risk) are required to be reported to the DSMB, the institutional REB and Health Canada. Expected, unrelated and/or non-serious adverse events will not be reported to the DSMB and the institutional REB. Reportable SAEs will be reported within 24 hours of the site becoming aware of the event

Should a clinically significant AE occur, the Study Medical Monitor will be notified. The monitor will require unblinding by the study pharmacist. The Investigator will be advised by the Medical Monitor and review with the parent/caregiver. Modifications may need to be made in the study sequence, for example, extending the time between dose increases. Any modifications in the protocol will be reflected on both the gabapentin and placebo arms.

Any AE that occurs between the time that a study participant is enrolled and the time that s/he departs the study at the end of the final study visit (or at the time of early discontinuation of the participant from the study for any reason) will be captured and recorded. At each contact with the participant, the investigator (or designate) must seek information on AEs by specific questioning and, as appropriate, by examination.

AEs that have been reported by the study participant will be followed-up for duration, intensity and possible recurrence.

All AEs (including SAEs) will be followed until resolution or until the investigator and the Medical Monitor agree that the AE has resolved, stabilized or become chronic and no further follow-up is required.

In the case of a Suspected Unexpected Serious Adverse Reactions (SUSARs) the Sponsor will expedite the reporting of the event to investigator(s), institutions(s), ethics board(s), and Health Canada per published guidelines. If the adverse reaction is not documented in the Product Monographs (new occurrence) and is thought to be related to the study treatment, the study sponsor may urgently require further information from the investigator for regulatory reporting.

